#### 7.1.3 Primary Endpoint with methods and timing for assessing recording and analysing variables

**The AUC of Wisconsin Upper Respiratory Symptom Survey (WURSS-21) during first 8 days of symptoms will be compared between both groups.**

WURSS-21 is a validated 3-dimensional structure questionnaire [12]. This survey has been demonstrated to be responsive, and valid to assessing the severity and functional impact of the common cold. It includes 10 items assessing symptoms (symptoms score, (items 2 to 11), 9 items assessing functional impairments (quality of life score, (items 12 to 20).) and 2 items assessing respectively global severity and global change. Brown et al. [13] support the practice of using, for AUC computation, a simply summed daily global illness severity score to represent the overall symptomatic and functional impairments arising from acute upper respiratory infection.

The WURSS-21 will be assessed in an e-diary once daily in the evening, taking into account the symptoms from the morning to the evening, during D2-D8 (day of the end of treatment). At D1, the WURSS-21 will be completed during the visit. After D8, the WURSS-21 will be assessed once daily until the subject feels not sick for two consecutive days.

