**Figure 1 : Flow chart of the study**

## 4. SAMPLE SIZE

A sample of 180 subjects (90 subjects per group) will be needed to provide 80% power with a one-sided test at a 0.05 significance level to detect a difference between Healsea® Rescue\* and Placebo groups AUC of 30%.

Assuming that approximately 10% of subjects may drop-out the study, 200 subjects will be randomly assigned at a ratio 1:1 to Healsea® Rescue\* and Placebo (100 subjects per group).

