### 6.3. Statistical/Analytical issues

#### 6.3.1. Significance level

All statistical analyses will be performed at the 0.05 global significance level (type I error rate), using one-sided tests.

The statistical results are conclusive for the primary efficacy criterion.

All the other statistical results have to be considered within a descriptive perspective and not as inferential issues. No adjustment for Type I error is done. P-values of statistical tests will be provided for information only.

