#### **6.4.7. AUC on scores of WURSS-21 questionnaire**

The computation of the AUC on any score of the questionnaire will be made for patients with non-missing value at D1 and at least another non-missing time point between D2 and D8. Otherwise, the AUC will be missing.

The AUC will be computed by the trapezoidal rule from D1 to D8 (Acute Phase).

If the value at D8 is missing, then it will be estimated by the value at the last non-missing time point before D8.

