## 12. CHANGES IN THE CONDUCT OF THE STUDY OR PLANNED ANALYSIS

The cold symptoms' duration was defined in the protocol as the number of symptomatic days between D1 and the first day the subject reports not having the symptom for two consecutive days.

Furthermore, since several patients still reported having symptoms while they reported they did not feel sick anymore at the question 1 during the two last days of completion of the WURSS-21 questionnaire, their positive answers to the cold symptoms' items have been considered as non-significant. Consequently, the question 1 has been taken into account instead of the corresponding items to determine the end of the cold symptoms' duration, however only on the condition that the two last days of completion were consecutive.

If the two last days of completion were not consecutive, positive answers to cold symptoms' items are still considered as symptomatic, even if the two last answers to the question 1 are negative. The symptom ends at the last symptomatic day if the patient reported the absence of this symptom after this day. Otherwise, the duration of the symptom is censored at D15 or at the end of the study, whichever occurs first.

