### 13.3. WURSS-21 questionnaire – Daily symptom report

Please complete the WURSS -21 in **the evening**, taking in account the symptoms from the morning to the evening, until you do not feel sick during two consecutive days (first question ticked NO during 2 consecutive days). In the case you already ticked “not sick” for 2 consecutive days during the TREATMENT PERIOD (D1 to Day 8), please do not complete the questionnaire either.

Please fill in one circle for each of the following items:

	Not sick 0	Very mildly		Mildly		Moderately		Severely	
	0	1	2	3	4	5	6	7	
How sick do you feel today?	0	0	0	0	0	0	0	0	0

Please rate the **average severity of your cold symptoms over the last 24 hours** for each symptom:

	Do not have this symptom 0	Very mild		Mild		Moderate		Severe	
	0	1	2	3	4	5	6	7	
Runny nose	0	0	0	0	0	0	0	0	0
Plugged nose	0	0	0	0	0	0	0	0	0
Sneezing	0	0	0	0	0	0	0	0	0
Sore throat	0	0	0	0	0	0	0	0	0
Scratchy throat	0	0	0	0	0	0	0	0	0
Cough	0	0	0	0	0	0	0	0	0
Hoarseness	0	0	0	0	0	0	0	0	0
Head congestion	0	0	0	0	0	0	0	0	0
Chest congestion	0	0	0	0	0	0	0	0	0
Feeling tired	0	0	0	0	0	0	0	0	0

Over the last 24 hours, how much has your cold interfered with your ability to:

	Not at all 0	Very mildly		Mildly		Moderately		Severely	
	0	1	2	3	4	5	6	7	
Think clearly	0	0	0	0	0	0	0	0	0
Sleep well	0	0	0	0	0	0	0	0	0
Breathe easily	0	0	0	0	0	0	0	0	0
Walk, climb stairs, exercise	0	0	0	0	0	0	0	0	0
Accomplish daily activities	0	0	0	0	0	0	0	0	0
Work outside the home	0	0	0	0	0	0	0	0	0
Work inside the home	0	0	0	0	0	0	0	0	0
Interact with others	0	0	0	0	0	0	0	0	0

Live your personal life	0	0	0	0	0	0	0	0
-------------------------	---	---	---	---	---	---	---	---

**Compared to yesterday, I feel that my cold is...**

Very much better	Somewhat better	A little better	The same	A little worse	Somewhat worse	Very much worse
0	0	0	0	0	0	0

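### Patients who feel 'not sick' before D8 appear free to stop the WURSS-21; SAP 6.4.7 then holds their last total flat to D8, which can shrink the AUC difference by an amount the documents leave unknown

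*SAP*

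**What the plan says.** Four places bear on this.

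- **Schedule.** Protocol 7.1.3: "The WURSS-21 will be assessed in an e-diary once daily in the evening", through D8. The 'not sick' stop is described only for the time after D8. Protocol 7.4.1 and the synopsis agree.
- **Patient page.** SAP 13.3 asks for completion until two consecutive 'not sick' days. For a patient who has already reached that point, it continues: "during the TREATMENT PERIOD (D1 to Day 8), please do not complete the questionnaire either".
- **AUC rule.** SAP 6.4.6 leaves wholly uncompleted days missing. SAP 6.4.7 applies the trapezoidal rule from D1 to D8 and adds: "If the value at D8 is missing, then it will be estimated by the value at the last non-missing time point before D8". SAP 10.1 defines the total as the sum of items 1 to 20. 'Not sick' is a zero on item 1 alone.
- **Residual symptoms.** SAP 12 records that several patients still scored symptoms while answering 'not sick'. For symptom duration, "their positive answers to the cold symptoms' items have been considered as non-significant". No matching rule exists for the AUC.

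Protocol 8.9 speaks only of interpolation. That gives no value for a patient with no later score.

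**The concern.** A patient who stops on day k (the second 'not sick' day) has no score on the remaining days up to D8. The SAP fills them in effect with the day-k total, including any residual symptom and function scores. In a self-limiting illness those would usually have gone on falling: Protocol section 4 says 75% of persons have a reduction or resolution of symptoms within 7 days. The earlier the stop, the more days carry the plateau.

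Protocol 5.1 expects faster recovery with the device, so more device patients would stop early and have more days filled. The number of filled days is a consequence of treatment, so randomisation and blinding do not balance it. At stake are the estimate and the power for the AUC of the total score, the only result that SAP 6.3.1 treats as conclusive.

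**Working it through.** **The plan's own figure.** SAP 4 takes 90 per group "to provide 80% power with a one-sided test at a 0.05 significance level to detect a difference between" the groups of 30% in AUC. Neither document gives a mean or SD for the AUC, so 180 cannot be reproduced directly. Solving backwards, 90 per group at one-sided 0.05 and 80% power means a standardised difference d = 0.371. A 30% reduction then implies SD/control mean = 0.30/0.371 = 0.81. The drop-out step reproduces: 180/(1 - 0.10) = 200.

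**Excess for one patient.** With last total r on day k, the area after day k is:
- flat to D8: r(8 - k)
- zero from the next day: r/2
- linear fade to zero over three days (k ≤ 5): 1.5r

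Flat therefore exceeds zero-from-next-day by r(7.5 - k), and exceeds the fade by r(6.5 - k). With k = 4 and r = 6 that is 21 and 15 AUC units. With k = 4 and r = 0 both are 0.

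**Two assumed records, D1 to D8.**
1. Totals 45, 32, 22, 14, 8, stop at D5.
   - Flat: (45 + 8)/2 + 32 + 22 + 14 + 8 + 8 + 8 = 118.5.
   - Decline continuing 5, 3, 2: (45 + 2)/2 + 32 + 22 + 14 + 8 + 5 + 3 = 107.5.
   - Zero after D5: 45/2 + 76 = 98.5.
   - Against the continued decline, flat errs by +10% and zero by -8%.
2. Totals 40, 20, 12, 10, stop at D4.
   - Flat: (40 + 10)/2 + 20 + 12 + 10 + 10 + 10 + 10 = 97.0.
   - Decline continuing 6, 4, 2, 1: (40 + 1)/2 + 20 + 12 + 10 + 6 + 4 + 2 = 74.5.
   - Zero after D4: 40/2 + 42 = 62.0.
   - Flat errs by +30% and zero by -17%.

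**Effect on the comparison.** Every input here is an assumption, since the documents give no score distribution.
- D1 total: lognormal, median 45, log-SD 0.5.
- Exponential decline: half-life lognormal, median 2.5 days, log-SD 0.4, multiplied by 0.65 for the device.
- Daily noise: log-SD 0.25.
- Personal 'not sick' threshold: median 4, 8, 12 or 16 out of 140, log-SD 0.4.
- 200,000 patients per arm. The diary stops after two consecutive days below the threshold.

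Power with 90 per arm is approximately Φ(d√45 - 1.645).

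| Median threshold | Stopped before D8, placebo / device | Reduction in mean AUC, full diary → flat | d, full diary → flat | Power, flat | d, zero rule |
|---|---|---|---|---|---|
| 4 | 15% / 41% | about 25.5% → 25.0% | 0.471 → 0.467 | 93.2% | 0.472 |
| 8 | 36% / 66% | about 25.5% → 24.1% | 0.474 → 0.460 | 92.5% | 0.471 |
| 12 | 54% / 80% | about 25.5% → 22.8% | 0.477 → 0.454 | 91.9% | 0.457 |
| 16 | 67% / 87% | about 25.5% → 21.3% | 0.472 → 0.441 | 90.5% | 0.429 |

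With the full diary, power is about 94% (d = 0.471: 3.160 - 1.645 = 1.515, 93.5%). The standardised loss is 1 - 0.467/0.471 = 1% in the first row and 1 - 0.441/0.472 = 7% in the last. It is smaller than the loss in the percentage reduction because the flat rule lifts the lowest AUCs and so also narrows the spread.

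**At the plan's design point.** If the same proportional losses applied to d = 0.371, it would become 0.368 to 0.346, and power would fall from 80% to about 79% to 75%.

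**Second set of assumptions.** Gamma-distributed starting totals and decline rates, 12 settings, 40,000 per arm. The faster arm had the larger excess every time. At a true reduction of about 31%, the flat rule gave 30.5%, 30.1%, 28.5% and 27.3% for thresholds 4, 8, 12 and 16.

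**The case against.** **The page may concern follow-up only.** Its last sentence can be read as telling patients already recovered by D8 not to fill in the form afterwards. The protocol's schedule fits that reading. So does SAP 7.2, which expects daily calls for non-completion in D1-D8 and treats lack of a score near D8 as a major deviation, with no exemption for recovered patients. The reading is possible. It does not fit the page's unqualified opening instruction, nor the SAP 7.2 minor deviation that counts missing scores only until recovery. What stands is that the texts conflict, and that the calls may keep early stopping rare.

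**SAP 12 does not locate the problem in D1-D8.** It concerns the last two days of completion, which can fall as late as D15, and gives no number of patients, size or day. A reader might infer that non-zero totals at stops before D8 are documented. They are not; SAP 12 shows only that such answers occur.

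**The harm is easily overstated.** The drop from 25.5% to 21.3% is about one sixth of the effect (4.2/25.5), and a reader might take that as the loss of power. The standardised loss in the same setting is 7%. That setting also has 67% and 87% of patients stopping before D8, which no document supports.

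**Zero after recovery is not clearly better.** It understates the two records by 8% and 17%. At the highest threshold its standardised difference is below that of the SAP rule (0.429 against 0.441). It also moves the estimate in the device's favour. SAP 12 is written in the past tense, so diary data had been seen, and a new primary rule now would look post hoc. This stands, and it limits the zero rule to a sensitivity analysis.

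**Conclusion.** The point holds as a conflict between documents with a conservative bias of unknown size. It needs three things: patients who stop before D8, last totals above zero, and scores that would have kept falling. Given these, the AUC is overstated, generally more in the faster-recovering arm. That ordering could reverse only if the faster arm's last totals were lower by enough to offset its extra filled days.

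Under the assumed inputs the relative reduction loses about 0.4 to 4 points and the standardised difference about 1% to 7%. With all last totals at 0 there is no error.

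A reader might infer that the rule threatens a false positive result or favours the device. The documents do not support that: with no treatment effect the rule treats both arms alike, and with a benefit it pulls the difference towards zero. Nor do they show that SAP 6.4.7 must be replaced as the primary rule.

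**What to change.** (a) Reconcile the patient page with Protocol 7.1.3 and 7.4.1: require the WURSS-21 every day through D8 whatever the answer to item 1, and apply the 'not sick' stop only after D8. This helps only patients who still have diaries to complete.

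(b) Keep SAP 6.4.7 as the primary rule. Before unblinding, add a sensitivity analysis of the primary AUC: a patient with item 1 at zero on two consecutive days before D8 and no later WURSS-21 is scored 0 from the day after the second such day to D8. Report by arm how many patients stopped before D8 and the distribution of their last totals. That table shows directly whether the issue matters.

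The cost is a few more diary entries for recovered patients, one extra AUC run and one small table. The zero rule understates true residual symptoms, and the two analyses need not bracket the truth if symptoms return after the stop, so the SAP should say so.

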## 7. STUDY PATIENTS

### 7.1. Disposition of patients

Screened subjects (signed informed consent) and included subjects will be summarised using frequencies and percentages as well as reasons of non-selection/non-inclusion, if applicable. The number and percentage of subjects who withdrew prematurely after inclusion, are lost to follow-up as well as the number of completers will be described by treatment group and overall. All withdrawn subjects after their inclusion will be described regarding their main reason for withdrawal.

### 7.2. Protocol deviations

Protocol deviations will be discussed during the data review meeting and the status (minor or major) of these deviations will be validated in order to identify the subjects to be excluded from the Per-Protocol Set.

Major deviations are defined by:

- Non-compliance with the inclusion or exclusion criteria;
- No assessment of the primary efficacy criterion (WURSS-21) at D1, D4±1 and D8-1 during the treatment period;
- Intake of forbidden medication, i.e. local or systemic corticosteroids, non-steroidal anti-inflammatory drugs (NSAID) or saline nasal spray;
- Intake of wrong treatment, i.e. wrong treatment given to the patient after randomization;
- A compliance to study product intake below 80% or greater than 120%.

All other deviations will a priori be considered as minor, e.g.:

- Telephone call or V2's dates that do not conform with the flow chart of the study;
- Telephone call or V2 not performed;
- Daily phone call to the subjects (in case of WURSS-21 non-completion) not performed (between D1 and D8);
- Treatment stopped before or after D8 morning (less or more than 14 intakes of study product);
- Non-compliance regarding the informed consent form;
- WURSS data missing (but data available at D1, D4±1 and D8-1) until subject's recovery (two consecutive and negative – “not sick” – answers to the first item) or D15/subject's end of study, whichever occurs first.

Major and minor deviations and their types will be described by treatment group and overall. They will be summarised with frequencies and percentages. Subjects will be counted only once within each type of deviation and within each category (major/minor).

A listing of all deviations will be provided for all included subjects, including the category.

### 7.3. Data Sets Analysed

The number and percentage of subjects in each analysis data set, as described in §5, will be provided.

## 8. DEMOGRAPHIC AND OTHER BASELINE CHARACTERISTICS

All demographic and baseline characteristics will be described on the Safety Set, by treatment group and overall.

### 8.1. Demographic characteristics

Age (years) and sex will be summarised using descriptive statistics already mentioned in §6.2.

### 8.2. Previous and concomitant medications

Previous and concomitant medications (taken at least once before reference start date) are coded by ATC class and substance name using the WHO-DRUG dictionary version 2022 Q1.

They will be summarised with frequencies and percentages.

Subjects will be counted only once within these ATC categories.

### 8.3. Medical and surgical past history

Medical and surgical past history is coded using the MedDRA dictionary version 25.0 and are classified by System Organ Class and Preferred Term.

The number and percentage of subjects with at least one medical and surgical past history of each category (SOC/PT) will be given.

Subjects will be counted only once within these categories.

### 8.4. Symptom's score of acute rhinitis

Symptoms' scores of acute infectious rhinitis will be described at baseline.

For each symptom's score, a Student (or Wilcoxon if the normality assumption is not acceptable) between-groups test will be performed.

### 8.5. Total Score of WURSS-21 at baseline

Total score of WURSS-21 (the sum of the scores of the twenty first items of the WURSS-21 questionnaire) will be described at baseline.

A Student (or Wilcoxon if the normality assumption is not acceptable) between-groups test will be performed.

### 8.6. COVID-19 antigen test at baseline

The results in each group of the COVID-19 antigen test performed at baseline will be described and compared by means of chi-square or exact Fisher test.

## 9. COMPLIANCE

Compliance will be calculated according to the following formula and analysed on the Safety set, by treatment group and overall.

The compliance will be calculated as follows:

**Compliance (%) = [Initial weight of the container (g) – Real weight of the container at the end of the study (g)] × 100 / [Initial weight of the container (g) – Theoretical weight of the container at the end of complete study (g)]**

with:

- Initial weight of the container = 33g;
- Theoretical weight of the container at the end of complete study = 27.7g;

i.e.:

$$\text{Compliance} (\%) = \frac{(33 - \text{weight}_{\text{end}}) \times 100}{5.3}$$

with  $\text{weight}_{\text{end}}$  the real weight of the container at the end of the study in g.

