### 3.7 Devices description

#### 3.7.1 Investigational device

Healsea® Rescue\* is a nasal spray (available in 20mL) using the APF (Advanced Preservative-Free) technology. This is a spray pump consisting of a white high density polyethylene bottle and a manual polyolefine/homopolymer polypropylene actuator holding the nozzle spraying the solution in the nostrils. A single activation propels a volume of  $100 \pm 20 \mu\text{L}$  of solution.

This is a non-sterile device. The primary packaging is described in Figure 1.

Figure 1 : The spray pump

The sponsor certified that the Healsea® Rescue\* Medical Device:

- does not contain any human blood derivative,
- does not contain any medicinal product,
- is not manufactured using tissues of animal origin.

As summarized below, Healsea® Rescue\* is intended to be used on nasal mucosa. The duration of use is 7 days.

Table 3 : Contact with body and total duration treatment

Type of contact	Device in contact with a surface
Type of tissues	Mucous membranes
Total duration treatment	It can be used for 7 days

**Healsea Rescue\*** and the **Placebo** need to be indistinguishable in the context of a blinded study. The subcontractor in charge of the blinding will remove the label of Healsea® Rescue\* and replace it by a white label with the mentions requested by the regulation.

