### 7.2 Investigational device and comparator

#### 7.2.1 Description of the exposure to the investigational device

The investigational device will be **Healsea® Rescue\***. This is a CE marked Medical Device used for acute infectious rhinitis and administered by spraying 2 puffs in each nostril 2 times per day during 7 days (14 intakes of the investigational device).

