The investigator will provide the patient with the device according to the treatment number as per randomization and explain how to use it. The investigator will also prime the pump bottle to identify a

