## **12. Device accountability**

The device accountability will be performed all over the study according to the SOP “Investigational Product Management” of the CRO. Briefly, the site will complete an accountability log after each receipt of the Medical Device and delivery to subject. The CRA in charge of the site monitoring will check the accountability log at each visit. At V2, the accountability log will be completed with the weight of the returned device by the subject.

Return of unused or expired investigational devices to the sponsor will be tracked using a specific record.

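### Compliance is computed from one fixed 33 g start weight and a 5.3 g target that does not match the stated regimen, so patients near the 80% and 120% Per-Protocol limits can be misclassified (supportive analysis only)

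*SAP*

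**What the plan says.** SAP 9 defines compliance as the weight lost by the bottle divided by the weight expected to be lost. Both reference weights are constants: "Initial weight of the container = 33g" and "Theoretical weight of the container at the end of complete study = 27.7g". The formula becomes (33 − returned weight) × 100 / 5.3, and it is "analysed on the Safety set, by treatment group and overall", with no value specific to an arm or a bottle.

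At Visit 1 (Protocol 7.4.1), "The investigator will also prime the pump bottle to identify a" possible malfunction. The number of priming sprays is not given. At Visit 2, according to Protocol 12, "the accountability log will be completed with the weight of the returned device by the subject"; neither document describes a weight at dispensing. After a device failure, Protocol 7.4.1 has both bottles weighed.

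On the device, Protocol 3.7.1 states "A single activation propels a volume of" 100 ± 20 µL, and Protocol 7.2.1 gives the regimen as "spraying 2 puffs in each nostril 2 times per day during 7 days (14 intakes of the investigational device"). Protocol 3.1 lists 27 g/L NaCl plus 0.4 g/L Symbiofilm for the active solution and 9 g/L NaCl for the placebo. The bottle is a nominal 20 mL in both arms.

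SAP 7.2 counts as a major deviation "A compliance to study product intake below 80% or greater than 120" per cent. SAP 5 removes patients with major deviations from the Per-Protocol Set, which serves as support for the primary AUC and for the two sub-score AUCs.

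**The concern.** A fixed start weight is safe only if every bottle leaves the site at that weight. The documents give three reasons why it may not: priming removes liquid before the patient's first use, bottle fill may vary, and the two solutions contain different amounts of solute. Whatever separates the true start weight from 33 g goes straight into the compliance figure.

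There are two further gaps. The 5.3 g target can be compared with the regimen and the pump volume, and it does not agree with them. The formula also has one start weight and one end weight, so it gives no rule for the two-bottle case that the protocol foresees.

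At stake are membership of the Per-Protocol Set near its limits and the compliance table by arm.

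**Working it through.** **Inputs from the documents.** Start 33 g; theoretical end 27.7 g; limits 80% and 120%; 0.1 mL per spray (0.08 to 0.12 mL); 20 mL bottle.

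**Assumptions, not in the documents.** Density 1.0 g/mL unless stated; a density gap of 0.010 to 0.013 g/mL between the solutions; 5 or 8 priming sprays as examples.

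**1. The plan's own figure.** 33 − 27.7 = 5.3 g, so the subtraction is right. The limits correspond to:
- 80%: 0.8 × 5.3 = 4.24 g lost, returned weight 28.76 g.
- 120%: 1.2 × 5.3 = 6.36 g lost, returned weight 26.64 g.
- Half-width of the band: 0.2 × 5.3 = 1.06 g.

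**2. Target against regimen.** 2 sprays × 2 nostrils × 2 per day × 7 days = 56 sprays, and 56 × 0.1 mL = 5.6 mL, or 5.6 g. Full nominal use therefore reads 5.6 / 5.3 = 105.7%. In sprays, the limits are 42.4 and 63.6, so the band accepts true use of 42.4 / 56 = 75.7% to 63.6 / 56 = 113.6%. For example, 16 intakes (64 sprays, 114.3% of plan) read 6.4 / 5.3 = 120.8%, a major deviation even with no priming.

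**3. Priming, if 33 g is the unprimed weight.** Each spray adds 0.1 / 5.3 = 1.9 points. For a patient who takes exactly 56 sprays after k priming sprays, the reading is (56 + k) × 0.1 / 5.3:

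| k | Reading at full use | True use accepted by 80–120% |
|---|---|---|
| 0 | 105.7% | 75.7–113.6% |
| 5 | 115.1% | 66.8–104.6% |
| 8 | 120.8% | 61.4–99.3% |

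Full nominal use leaves 6.36 − 5.6 = 0.76 g below the upper limit. The priming shift is nearly the same in both arms.

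**4. Difference between arms.** With equal fill volume, what separates the returned weights at full use is the liquid still in the bottle: 20 − 5.6 = 14.4 mL.
- 0.010 × 14.4 / 5.3 = 2.7 points; 0.013 × 14.4 / 5.3 = 3.5 points. Active reads lower.
- With filling to equal weight, only the sprayed 5.6 mL differs: 0.010 × 5.6 / 5.3 = 1.1 points; 0.013 × 5.6 / 5.3 = 1.4 points. Active reads higher.

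**5. Pump tolerance.** 56 × 0.08 / 5.3 = 84.5% and 56 × 0.12 / 5.3 = 126.8%. This spread at full use has nothing to do with the start weight.

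**The case against.** The strongest reply is that the consequences are limited and much of the mechanism is conditional.

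- **33 g may already be the post-priming weight.** SAP 9 does not say. If it is, step 3 falls away. This stands, and it is why the priming figures are given only as conditional.
- **5.3 g may come from weighing real bottles.** It corresponds to 5.3 / 56 = 0.095 g per spray, inside the pump tolerance. That is possible, but neither document says so, and the nominal figures do not reproduce it.
- **The primary result does not depend on compliance.** This stands. The primary and secondary analyses use the Full Analysis Set, which is not defined by compliance, and SAP 5 calls the Per-Protocol analysis supportive.
- **The blind data review validates deviations.** A general upward shift might be noticed there, but no rule tells the meeting how to handle it.
- **The CRO procedure on product management may require a dispensing weight.** Protocol 12 only summarises that procedure. Even so, SAP 9 would still insert 33 g.

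A reader might go further and infer that the rule does misclassify patients, and does so differently by arm. The documents do not establish that: the priming count, the fill method and the densities are all unstated, and priming moves both arms together. Nor is the salt difference of 18 g/L × 0.020 L = 0.36 g the difference in bottle weight. Both solutions are made up to volume, so salt takes the place of some water; the assumed density gap gives 0.20 to 0.26 g per 20 mL. Dividing that by 5.3 g gives 3.8 to 4.9 points, which overstates the gap at full use because 5.6 mL has by then left the bottle.

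**Conclusion.** The point holds as a cheap improvement to a supportive analysis. One constant start weight, combined with priming, possible fill variation and solutions of different solute content, can misclassify patients near 80% or 120%.

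The part that rests most directly on the documents is the mismatch between 5.3 g and 56 × 0.1 mL: full nominal use reads 105.7%, with density 1.0 g/mL as the only assumption. Priming could add 1.9 points per spray in both arms if 33 g is the unprimed weight. The arm gap is smaller and its direction is unknown: active about 2.7 to 3.5 points lower under equal fill volume, or about 1.1 to 1.4 points higher under equal fill weight, on the assumed densities. A shift of that size matters only for patients already close to a limit.

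There is no ground to infer bias in the primary result.

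**What to change.** **If bottles can still be weighed before dispensing:**
- Weigh each bottle at Visit 1, after priming and before it is handed over, and enter the weight in the accountability log.
- In SAP 9, replace 33 by that bottle's own Visit 1 weight. After a replacement, sum the weight lost over both bottles.
- Reconcile the 27.7 g theoretical end weight, and hence the 5.3 g, with the regimen in Protocol 7.2.1 and the pump volume in Protocol 3.7.1, and state the source of the figure kept. Without this step, full nominal use would still read about 106%.

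**If bottles are already dispensed** (SAP 12 describes diary answers that patients have given, so this may be the case): state whether 33 g is before or after priming. Before database lock, and without using allocation, report how Per-Protocol membership changes over a plausible range of start weights. For example, 31.7 to 33.3 g covers up to ten priming sprays (1.0 g) below 33 g and 0.26 g either way for density. The reconciliation of 5.3 g and the rule for replaced bottles are needed here too.

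**Cost.** One extra weighing per patient, one log column and one changed formula. The pump tolerance of ±20 µL remains, as does a small density-related arm gap of about 1.1 to 1.4 points at full use (5.6 mL × 0.010 to 0.013 g/mL / 5.3).

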**Strictly Confidential**

possible malfunction before the patient leaves the site. In case of dysfunction, a new randomisation number and a new treatment will be attributed to the patient using the eCRF back-up randomisation module.

*NB: The first use of the device will be performed in the evening of the Day 1.*

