**D8 (Telephone Call):**

The investigator or his/her delegated designee will call the patient to remind him/her to stop the treatment.

➤ *NB: The last study nasal spray intake will be performed in the morning of the Day 8.*

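### Does the 5.3 g that SAP section 9 counts as full use conflict with the protocol's 56 sprays of nominally 100 µL?

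*SAP*

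**What the plan says.** SAP section 9 divides the observed weight loss by a fixed theoretical loss. The two constants are "Initial weight of the container = 33g" and "Theoretical weight of the container at the end of complete study = 27.7g", and the printed formula has 5.3 in the denominator. No spray count, spray volume, density or source is given for either weight.

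The protocol describes the same regimen in sprays. Section 7.2.1 has "2 puffs in each nostril 2 times per day during 7 days (14 intakes of the investigational device"). Section 7.4.1 confirms the count of 14: under Visit 1, "The first use of the device will be performed in the evening of the Day 1", and under the D8 call, "The last study nasal spray intake will be performed in the morning of the Day 8". On the pump, section 3.7.1 states "A single activation propels a volume of" 100 ± 20 µL, and section 3.7.2 gives the placebo the same pump technology.

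The percentage is used in SAP section 7.2, where "A compliance to study product intake below 80% or greater than 120"% is a major deviation. Major deviations lead to exclusion from the Per-Protocol Set (SAP section 5). The same section 7.2 lists as minor "Treatment stopped before or after D8 morning (less or more than 14 intakes of study product").

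**The concern.** The regimen and the nominal spray volume give 5.6 mL for full use, yet the SAP treats 5.3 g as full use. A reader who multiplies out the protocol's figures does not reach the SAP's constant, and neither document explains the gap. The SAP also does not say whether 33 g is the weight before or after the investigator primes the pump at Visit 1.

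If the denominator is too small, every patient's compliance is overstated by the same factor. Some under-users would then stay in the Per-Protocol Set, and some moderate over-users would be removed from it, at cut-offs other than the stated 80% and 120%. The blind data review would be working from those percentages.

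**Working it through.** **Inputs.** 2 puffs × 2 nostrils × 2 times a day × 7 days = 56 sprays, or 14 intakes × 4 (Protocol 7.2.1). 100 µL nominal, 80 to 120 µL tolerance (Protocol 3.7.1). 33 g and 27.7 g (SAP 9). Limits of 80% and 120% (SAP 7.2). The documents give no density; 1.00 g/mL is assumed, with 1.02 as a sensitivity value.

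**The plan's own figure.** 33 − 27.7 = 5.3 g, so the subtraction is right. Per spray: 5.3 / 56 = 94.6 mg.

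**Nominal delivery.** 56 × 0.100 mL = 5.6 mL, which is 5.60 g at 1.00 g/mL and 5.71 g at 1.02.
- Score for full use: 5.60 / 5.3 = 105.7% (5.712 / 5.3 = 107.8% at 1.02).
- Lower limit as a share of the regimen: 80 × 5.3 / 5.6 = 75.7%.
- Upper limit: 120 × 5.3 / 5.6 = 113.6%.

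**Who changes status** (100 mg per spray, start weight 33 g):

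| Intakes | Loss (g) | Score with 5.3 g | Score with 5.6 g | Status |
|---|---|---|---|---|
| 10 | 4.0 | 75.5% | 71.4% | out under both |
| 11 | 4.4 | 83.0% | 78.6% | in / out |
| 12 | 4.8 | 90.6% | 85.7% | in under both |
| 14 | 5.6 | 105.7% | 100.0% | in under both |
| 15 | 6.0 | 113.2% | 107.1% | in under both |
| 16 | 6.4 | 120.8% | 114.3% | out / in |
| 17 | 6.8 | 128.3% | 121.4% | out under both |

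**Where those changes begin.** With 5.3 g, 11 intakes are kept only if the mean spray is at least 0.8 × 5.3 / 44 = 96.4 mg. Sixteen are excluded only above 1.2 × 5.3 / 64 = 99.4 mg. At 94.6 mg, 11 intakes score 11/14 = 78.6% and 16 score 16/14 = 114.3%, so both are classified as the rule intends.

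**Would 5.6 g do better?** It is right only if the mean spray weighs 100 mg, which is not documented either. The arms contain 27 and 9 g/L of salt (Protocol 3.1.1 and 3.1.2), so their densities differ. Suppose for illustration they were 1.02 and 1.00 g/mL. At 100 µL and a 5.6 g denominator, 11 intakes score 44 × 0.102 / 5.6 = 80.1% in one arm and 78.6% in the other, so the same behaviour is kept in one arm and excluded in the other. With 5.3 g the scores are 84.7% and 83.0%, both kept. The 5.3 g constant has a similar split elsewhere, at outputs between 96.4 / 1.02 = 94.5 and 96.4 µL. Neither constant is free of the problem.

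**Priming.** If 33 g is the weight before priming, each priming spray adds 0.1 / 5.3 = 1.9 points. Three would add 5.7 points, as much as the whole gap between 5.3 and 5.6 g. The number of priming sprays is not given, so a recalculation from nominal volume would not settle the constant.

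**The case for a change.** The best case for a change is that 5.6 g fits the device specification and 5.3 g does not. Across 80 to 120 µL, a fully adherent patient scores 4.48 / 5.6 = 80.0% to 6.72 / 5.6 = 120.0%, which are exactly the stated limits. With 5.3 g the range is 84.5% to 126.8%, so a patient who takes every dose from a bottle averaging more than 1.2 × 5.3 / 56 = 113.6 mg per spray becomes a major deviator. A density above 1.00, or priming counted as use, pushes in the same direction. A constant that decides Per-Protocol membership ought also to be traceable, and checking it costs almost nothing.

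The arithmetic stands, and so does the point on traceability. The step to a wrong constant does not. The protocol states the ±20 µL for a single activation; nothing in the documents says that a bottle's mean over 56 sprays reaches those extremes. A weighed mean of 94.6 mg is a plausible origin for the figure, and its record may sit in the CRO's product-management procedure, to which Protocol sections 3.4 and 12 refer. Its absence from the SAP is missing detail, not a contradiction. There is also a cost to changing it: SAP section 12 already describes answers that several patients gave, so a new constant might be chosen when return weights are known.

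**Conclusion.** No change to the plan is needed. The gap is 0.3 g in 5.6 g, and 5.3 g corresponds to a spray output within specification. The 75.7% and 113.6% limits hold only for a mean of exactly 100 µL, a density of 1.00 g/mL and a start weight of 33 g. If the true mean is 94.6 mg, the stated limits act as written.

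The reach is small even in the unfavourable case. Of the whole-intake counts checked, only 11 and 16 move, and 16 requires continued use despite the D8 call to stop. Compliance feeds the compliance table and the Per-Protocol analyses of the total and sub-score AUCs. SAP section 5 calls the Per-Protocol analyses supportive, and SAP section 6.3.1 treats only the primary criterion as conclusive. The primary analysis on the Full Analysis Set does not use compliance. How many patients would move cannot be worked out from the documents.

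Deviation status is also not automatic. SAP section 7.2 has it validated at the data review meeting, and Protocol section 9.3 gives the blind review the task of defining the analysis populations. Where the two weights come from, and whether 33 g is before or after priming, are factual questions the team can settle there from the accountability records. Following SAP section 9 as written is not shown to give a wrong result.
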